At the DCC, electronic data are backed up daily or weekly to a backup server depending upon the receipt of data. Additional backup external hard drives are stored in a fireproof safe. Protected Health Information (PHI) is confined to a secure device that is not connected to the internet. All computers are password protected and the whole drive is encrypted with Bitlocker encryption. They are on a non-routable LAN network. No file and database servers are accessible to the public through the Internet. A hardware-based firewall device protects the network system against hackers and any unauthorized internet access. Spam and email filtering is built-in within the firewall device. The anti-virus software (McAfee Anti Virus) protects the network from threats of viruses, worms and Trojan horses and other malwares contained in email attachments and also from files downloaded through the internet. Through "push-technology" this anti-virus software is automatically updated for all virus definitions and other updates.

Confidentiality

The field coordinator will oversee the onsite assignment of individual IDs. These ID numbers will not contain PHI (e.g., social security number, medical records number, etc.) The list of assigned IDs with minimal PHI (name, date of birth and date of admission) is maintained in a locked cabinet at an on-site location during the course of data collection and later transferred to a secure cabinet at the DCC. Data-collection files will be identified only with coded IDs. In compliance with HIPAA, individual participant confidentiality will be assured using ID codes throughout data processing and analyses. Additionally, none of the analyses will permit identification of any individual by name. The interviewers will be aware of the linkage between individual and ID numbers. At the DCC, individual participants will be known only by their ID numbers, which will be used as the basis for communication with the interviewers in the event of data anomalies. The clinical/research barrier will remained intact, in that it is not necessary for any of the data-processing staff to be familiar with the identity of the participants. No PHI will be stored in devices linked to the internet.

Statistical methods

Statistical methods for primary and secondary outcomes

Analyses for the primary hypothesis for the distal outcome: The primary analyses will examine, on an ITT basis, the differences between the usual care and intervention groups in the reduction of falls/accidents/injuries over time. Other approaches, e.g., the analysis of the “as treated” sample can result in biased estimates of the causal treatment effect due to compromised random assignment. Our primary approach to analyses is guided by our own experience,⁵⁷ and reviews.^{58,59} Depending on the level of missing data, analytic strategies (see below) can be used to address non-compliance, e.g.⁶⁰ Based on prior trials that we have coordinated, sampled from this population, 1 year attrition is between 30% and 40%; thus for 6-month data (projected attrition of 15%), the ITT analyses of all subjects will be feasible. Longitudinal analyses will include those with at least baseline and one follow-up. Sensitivity analysis will be performed using multiple imputation under different assumptions for missing data.

Because randomization is at the facility rather than individual level, imbalance may be observed on baseline variables. Preliminary analyses will be performed to determine whether the groups are balanced. Two-tailed tests of significance will be performed. Binomial tests are to be conducted on dichotomous variables, Poisson tests on nonbinomial (e.g., count) data, and *t* tests on ordinal data, adjusting standard errors for clustered data within facilities; *p* values are reported because the design does not permit randomization at the level of the individual.

Effect on likelihood of falls/injuries/accident reduction:

Statistical methods appropriate for clustered data will be used in the primary analysis to compare the groups with respect to the binary outcome. Generalized mixed effects models (MEMs) will be used to test the hypothesis that those assigned to the intervention will experience a significantly higher rate of fall/accident/injury reduction as contrasted with usual care. The outcome will be modeled as a function of intervention, time and their interaction and controlling for the baseline falls. To account for the clustered nature of the outcomes, the models will include random effects for facilities, units and subjects. The models will be fit using mixed effects logistic-regression as implemented in SAS Proc Glimmix. The appropriate covariance structure will be determined. The primary analysis will be supplemented with an exploration of the effect of baseline subject, facility and unit characteristics on the intervention effect. These results will inform generalizability of

intervention effects.

Analyses for secondary outcomes: The proposed secondary outcomes are affect, measured by the FTQ and the NIH PROMIS depression measure,^{61,62,63} and behavior. The reliability estimates of the outcomes are typically at least 0.90. Methods for analyses of treatment effects in pre-post clinical trials, in the context of missing data, have been compared.^{64,65,66,67,68,69} The primary proposed analyses will use MEMs, and a full information likelihood approach, with sensitivity analyses using generalized estimating equations (GEE).

Statistical models: The primary endpoint analysis for comparison between the two groups with respect to various outcomes will be based on models for the outcome at 6 and 12 months as a function of the intervention condition, adjusting for the baseline value of the outcome, i.e. an ANCOVA-type MEM analysis with intervention as a factor with two levels and baseline value as a covariate. For multiple outcomes (e.g. NIH PROMIS and FTQ) MANCOVA-type MEMs will be used to simultaneously model the multiple outcome variables. An additional factor (domain) denoting the individual outcome variables will be included in the model together with interactions between domain (depression/affect measures) and intervention. A significant interaction term would indicate that the effect of the treatment is different for affect and depression; in that case two treatment effects will be estimated for each outcome. If the interaction is not significant a model with only main effects for depression/affect and treatment will be fit and the (common) treatment effect will be estimated from this model. In addition to significance testing, we will estimate the treatment effects with 95% CI. The MEMs allow modeling the correlation between the variables assessed on the same subject and that between subjects from the same units and facilities. Group differences in total scores will be examined using a linear mixed (fixed and random effects) model for effect estimation.

The use of SAS Proc MIXED will allow for the possible group heterogeneity in residual variances that may require modeling to satisfy model assumptions and improve model fit, and the modeling of the covariance structure. In secondary analyses, we will examine within subjects change over time. We did not perform power calculations for the secondary outcomes because the most

stringent power requirements are for the primary outcome. However, we will be able to detect relatively small effect sizes, given the sample size.

Examination of the exploratory potential mediating effects of behavior on the relationship between the R-REM intervention and the falls/injuries/accident outcome will be examined using mediation analyses. Although recent evidence from Monte Carlo studies support simple joint significance tests of the mediating path coefficients,^{70,71,72} also examined will be other formal tests of mediation effects.^{73,74}

Based on prior experience with the outcomes, it is not expected that transformations will be necessary. Baseline variables will be examined by study arm; however, no p values will be provided, and covariates (other than baseline values) are not proposed for inclusion in the main analyses of treatment effects.

Examination of potential region differences: Data from regions (upstate and downstate) will be combined and each outcome (e.g., depression, affect) modeled as a function of two factors (i) intervention, a factor with 2 levels and (ii) region, a factor with 2 levels, and the interaction between (i) and (ii). MEMs will be used for each outcome, e.g., depression, and likelihood ratio tests (χ^2) used to test for significance of the interaction term. The study is not powered to detect meaningful regional differences in treatment effect; therefore we will use $\alpha=0.15$ as a criterion, and explore if regional differences are related to differences in intervention effects.

Interim analyses

There are no plans for interim analysis or predetermined stopping guidelines.

Methods for additional analyses (e.g. subgroup analyses)

Heterogeneity of Treatment Effects (HTE): Because there is interest in examining subgroups to determine for which individuals interventions may be effective, we will perform descriptive HTE with potential effect modifiers as interaction terms. HTE will be examined for subgroups, e.g., those with and without cognitive impairment.

Methods in analysis to handle protocol non-adherence and any statistical methods to handle missing data

Examination of baseline differences on key variables between completers and those lost-to-follow-up will be conducted to inform about the nature of the missing data. The ITT analyses performed using MEMs will permit all individuals with at least one post-baseline observation to be included.

Depending on the level of missing data, analytic strategies can be used to address non-compliance, e.g.⁷⁵ For the sustainability analyses, analyses will be of those with at least baseline and one follow-up. Sensitivity analysis will be performed using multiple imputation under different assumptions for missing data. Examination of baseline differences on key variables between completers and those lost-to-follow-up will be conducted in order to inform about the nature of any missing longitudinal data. Methods of examining missing data, e.g., propensity scores, inverse probability, EM algorithm and multiple imputation sensitivity analyses will be considered. If substantial missing outcome data are observed, we will use a specific imputation approach, e.g., Markov Chain Monte Carlo procedures⁷⁶ depending on the amount and pattern of missing data. SAS Proc Multiple Imputation and MIAnalyze will be used. We will perform joint simultaneous imputation; at least 50 multiple imputations will be generated and PROC MIAnalyze will be used to combine the results and estimate the log-odds, adjusted standard errors, and significance.

Plans to give access to the full protocol, participant level-data and statistical code

There are no such plans at this time.

Oversight and monitoring

Composition of the coordinating centre and trial steering committee

The DCC at the RD-HHAR is responsible for oversight of data collection and analyses.

Composition of the data monitoring committee, its role and reporting structure {21a}

The Data Safety and Monitoring Board (DSMB) or data monitoring committee (DMC) is composed of five members including a chair, clinician/ safety officer, and a biostatistician. The NIA project

officer will also attend DSMB meetings. The DSMB responsibilities include: review the research protocol, informed consent documents and plans for data safety and monitoring; evaluate the progress of the trial, including periodic assessments of recruitment, accrual and retention, participant risk versus benefit, performance of the trial sites, and other factors that can affect study outcome; review study performance, make recommendations and assist in the resolution of problems reported by the principal Investigator; protect the safety of the study participants; report to NIA on the safety and progress of the trial; and ensure the confidentiality of the study data and the results of monitoring. The Board acts independently from the study sponsor.

Adverse event reporting and harms

All adverse events (AEs) and severe adverse events (SAEs) will be reported by the interviewers to the Project Manager who will update the Adverse Events Reporting Form and alert the PI.

Given that the study intervention is staff training, and there are no physical components to the participant evaluation (e.g., no blood draws or physical examinations), it is expected that no AE or SAEs will be related to study participation. Given that this is an older study population, SAEs (e.g., hospitalizations, death) are expected to occur, with no relationship to study participation.

Thus, per the NIA sample SAE/AE Process flow diagram, these events are not unexpected and will be reported to the DSMB at annual teleconferences. However, in the unlikely event that an AE or SAE is determined to be definitely, probably, or possibly related to the study it will be reported as follows: SAEs will be reported by the PI to the DSMB, NIA, and IRB within 24 hours of the event being reported to the Investigator; AEs will be similarly reported within two weeks of the event. Although there will be multiple assisted living facilities enrolled, it is unlikely that these participating sites will have their own IRBs; thus, there will not be site specific IRB notification beyond that to the Weill Cornell Medical Center and the Hebrew Home at Riverdale IRBs.

Plans for communicating important protocol amendments to relevant parties (e.g. trial participants, ethical committees)

Any protocol amendments will be presented first to the DSMB for approval. If approved, plans will

be presented to the IRB.

Dissemination plans

Study outcomes will be presented in manuscripts in relevant peer-reviewed journals and at scientific meetings. Depending on the wishes of the facility administrators, there may be a meeting for participating facilities staff to present study findings.

Abbreviations

AEs: adverse events

ALRs: assisted living residences

BRDS: Behavior Recognition and Documentation Sheet

CAPI: computer assisted personal interview

CAREDIAG: Care Dementia Diagnostic Scale

DCC: data coordinating centre

DSMB: Data Safety and Monitoring Board

FTQ: Feeling Tone Questionnaire

HTE: heterogeneity of treatment effects

INCARE: Institutional Comprehensive Assessment and Referral Evaluation

IRB: Institutional Review Board

ITT: intent-to-treat

LTSS: long-term services and support

MEMs: mixed effects models

NIA: National Institute on Aging

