The authors conducted the first systematic, prospective study of resident-to-resident elder mistreatment (R-REM) in nursing homes and have developed novel methodology to identify the phenomenon. Data demonstrated that (1) R-REM is highly prevalent, (2) case finding methodology is greatly enhanced by meaningful participation of front line staff, and (3) paradoxically, higher functioning residents may be at greatest risk for involvement in R-REM (e.g., residents who are ambulatory and capable of wandering as opposed to those who are in the last stages of dementing illness). Additionally, funded by the New York State Department of Health

dementia grants program we developed a three module-program targeting front line staff to implement best practices related to R-REM in long-term services and support (LTSS) settings. Using an experimental design, we tested the intervention in nursing homes. Evaluation of longitudinal outcomes showed significant increases in staff knowledge post training, controlling for pre-training levels for the intervention group and of increased recognition of R-REM, and longitudinal reporting in the intervention as contrasted with the usual care group.¹⁸ Additionally, falls, accidents and injuries were reduced.¹⁹ These findings have important implications for assisted living residences (ALRs) where residents typically have cognitive impairment with better mobility and less staff to intervene in R-REM. The state survey process is also less uniform in ALRs (in comparison to nursing homes) and has not addressed R-REM.

Objectives

The goal of the project is to evaluate a training program for staff that enhances identification and intervention with respect to episodes of resident-to-resident elder mistreatment (R-REM). The hypotheses corresponding to the specific process outcome aims (1 & 2) and primary distal outcome (aim 3) for which the study was powered are:

Aim 1 (A1). Enhance staff knowledge of R-REM

Hypothesis 1: Staff knowledge related to R-REM and R-REM treatment will increase after training.

Aim 2 (A2). Enhance staff recognition, reporting and care planning related to R-REM

Hypothesis 2: Due to the heightened awareness as a result of training, the frequency of reported R-REM in the intervention group will increase, relative to the comparison group after training.

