- C. A presentation of the SEARCH (**S**upport, **E**valuate, **A**ct, **R**eport, **C**are Plan, **H**elp to Avoid) approach to R-REM management; review, lessons learned; post-test.

The 25- minute film for this module was designed by the research team and directed and produced by the New York University Department of Media Production. It was narrated by distinguished journalist, [name], and includes a discussion of what constitutes putative evidence of serious abuse, such as bruises, cuts, or more serious injuries (broken bones or cracked ribs). Mistreatment such as verbal aggression and threats, sexual harassment and missing belongings are discussed. Three skits by professional actors are presented.

Skit 1: Most obvious form of elder mistreatment: physical assault; **Skit 2:** Less obvious form of elder mistreatment: verbal insult; **Skit 3:** Subtle form of elder mistreatment: psychological abuse, e.g. wandering uninvited into another's room and rummaging through another resident's property. Each skit is followed by an example of a poor staff response to the event as well as a better practice, and by commentaries by leading multidisciplinary experts in elder abuse, representing different perspectives: psycho-social, medical, nursing, administrator/legal.

The final component of the video is a review of nine steps to manage and curb R-REM.

Description of Module 3: Implementation of best practices related to R-REM

1. Introduction and review of previous session;
2. Presentation of implementation methods and forms (The R-REM Behavior Recognition and Documentation Sheet -- BRDS); discussion of methods for completion;
3. Presentation of filmed vignettes for practice in the completion of the BRDS;
4. Review practice sheets and lessons learned;
5. Review of implementation guidelines.

The focus of this session is on the intervention fidelity and implementation measures, including implementation of reporting guidelines. The training includes video vignettes that are rated and reviewed to confirm skills. Ways to enhance positive group relationships and the use of

community to counteract individual acts of mistreatment are discussed, addressing the question, How can staff work together to structure the social and physical environment to mitigate R-REM? The importance and rules for reporting R-REM are reviewed.

Criteria for discontinuing or modifying allocated interventions

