This measure was based on the Shift Coupon, a form originally designed by nursing staff to provide a “quick, easy, anonymous, and non-threatening method to report adverse events,”²¹ and is in the form of a small note pad. BRDSs are intended to measure recognition and capture real time R-REM events. Hypothesis 2, regarding enhanced R-REM recognition will be examined with a Chi-square analysis comparing counts of BRDS reports from experimental and comparison facilities captured over time, and treated as binary incidents. Reporting implementation will be examined by evaluating the differences between experimental and comparison group staff reports of R-REM, collected over three waves. Individual R-REM reporting will be determined by counting whether any of the staff-reported R-REM indicators are positive. The object of this analysis is not to identify individuals and perpetrators, but to examine the reported events. In modeling R-REM events, a Poisson regression of count data will be performed.

Aim 3: Primary level-4 evaluation of distal outcomes: Summary of the sources of data for determining falls/accidents/injuries and incidents of R-REM: The data used for evaluation of the primary distal outcome and for R-REM reports include (a) self-report among those residents who are capable, (b) Accident and Incident Reports, (c) resident record review, (d) observational data, including the BRDS, and (e) reports from staff. In addition, an environmental evaluation will occur. Data for falls and injuries will be collected via chart review, staff report and residents who can self-report, and from Incident/Accident Reports on an ongoing basis. Resident and staff informant information will be collected at baseline, 6- and 12-month follow-up. Falls will be considered as binomial (any fall) and Poisson distributed (fall counts).

Sample size {14}

Power calculations are provided for the primary distal outcome: falls, including accidents and injuries, also the outcome requiring the largest sample size. Upstate it is expected that an average

of 50 residents per site will be selected for a total of 300. Downstate, the facilities are larger, and it is expected that the average size will be 125 residents or 750 total. The proposed sample size is 6 facilities and 525 residents per arm.

Using the canonical link (Logit), the generalized linear model (GLIMMIX):

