Extended Interview: An extended Interview will be administered to participants with sufficient cognitive abilities to respond. Research has demonstrated that many residents can reliably self-report yes/no questions about daily care,³¹ life satisfaction,³² pain,³³ and quality of life.^{34,35,36} It is anticipated that about 70% to 80% of residents will be included at this stage. This interview includes scales of fear of falling/ falls history, depression/ affect, and ADLs.³⁷ The number of falls experienced in the past year and the Fear of Falling scale, comprised of eight items tapping feelings regarding fear of falling and the reasons for fear, will be administered. The alpha coefficient for this scale for a prior NY State Assisted Living sample was .84 at baseline and 0.85 at follow-up. Depression scales: The Short Care^{38,39,40,41,42} (alpha of 0.83 for an assisted living sample at baseline and 0.81 at follow-up) typical items are "feeling sad or depressed during the past month," "cried during the past month", and "lie awake at night with depressed thoughts." Included is an anchored four-point global rating of happiness level. We will also include the Patient Reported Outcomes Measurement Information System (PROMIS) Depression scale.⁴³

Resident to Resident Elder Mistreatment- Resident Version (R-REM-R): For residents who are capable, the R-REM-R will be used to determine whether an incident of R-REM has been directed at the respondent. This measure was created by the applicant team by combining desirable aspects of the most commonly used instrument in violence research⁴⁴ with a measure used to rate behavioral disturbance in LTSS.⁴⁵ The measure contains 22 items related to verbal, physical, sexual and other behaviors along with their frequency during the two weeks and the past year.

After focus groups with LTSS staff, more R-REM items were added and a follow-up distress question was added to all endorsed items. The Cronbach's alpha estimate for the scale was 0.90.

2. Staff Informant Interview

A brief Informant interview will be administered to the staff member most familiar with the participant.

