A. For each participant, ten five-minute observations are performed by trained interviewers at different times of the day and in different locations in order to obtain additional information about incidents of R-REM and other disturbed behaviours. While episodes of R-REM are likely to be brief and intermittent, based on our experience in the nursing home study, interviewers did observe many incidents of R-REM. The Total Observation Checklist includes 14 affect and 37 behaviour items (Observed Behavior Checklist).⁵³ Frequencies of affective and behavioural states are coded as: “Not at all”, “Very little (1 or 2xs during observation period)”, “With some frequency (several times)”, “With moderate frequency (many times but not continuous)”, or “With great frequency (continuous)”. Typical affect items include: “Crying”; “Agitated”; “Emotionally labile”. Typical behavioural items include: “Disruptive of others”; “Wandering”; and “Argumentative”. In an urban LTSS sample, the Cronbach’s alphas ranged from .74 to 0.85 and from 0.85 to 0.87 in a rural LTSS sample.⁵⁴

B. R-REM behavior recognition and documentation sheet (BRDS): This measure was based on the Shift Coupon, a form originally designed by nursing staff to provide a “quick, easy, anonymous, and non-threatening method to report adverse events,”⁵⁵ and was in the form of a small note pad. BRDSs are intended to measure recognition and capture real time R-REM events. These forms are designed as prescription pads to be carried in the pockets of staff. They are distributed at the training sessions (module 3 for intervention facilities and during the opening of the unit for usual care staff); additional pads are available at a central location. Sheets are torn off after documenting R-REM. Items include: residents involved, identity of the perpetrator, actions involved, location, potential cause, and what did you (staff) do about it. Boxes for completed forms are placed in a designated location on each unit.

C. Event logs: When an event is reported from a) resident interview b) staff interview c) interviewer observation, or d) BRDS, the research interviewer will complete an Event Log worksheet in order to better understand the circumstances of the R-REM event. This form contains descriptive

information about the event, its time and place, the reporting source, the participants, and environmental factors at the time of the event.

4. Chart data

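### Hypothesis 2 infers recognition from report counts, but those counts combine how often R-REM occurs with how often it is detected, and the plan does not separate the two

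*Combined protocol and SAP*

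**What the plan says.** The Objectives predict that "the frequency of reported R-REM in the intervention group will increase, relative to the comparison group after training", and name the cause of that rise in advance as greater awareness from the training.

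Outcomes, Aim 2, gives the tests. For recognition: "Hypothesis 2, regarding enhanced R-REM recognition will be examined with a Chi-square analysis comparing counts of BRDS reports from experimental and comparison facilities". For reporting, staff reports are compared between arms over three waves, and "Individual R-REM reporting will be determined by counting whether any of the staff-reported R-REM indicators are positive". A Poisson regression is planned for event counts. None of these has a term or denominator for the R-REM that actually took place.

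The same training is also meant to reduce R-REM. The Module 2 film closes with steps for controlling it, the SEARCH approach includes helping residents avoid it, and Module 3 asks "How can staff work together to structure the social and physical environment to mitigate R-REM". Under Aim 3, the second secondary hypothesis expects resident behavior problems to decline.

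The plan also collects R-REM information that does not come from staff. In residents who are capable, "the R-REM-R will be used to determine whether an incident of R-REM has been directed at the respondent", with items covering two weeks and the past year. Interviewers make ten five-minute observations per participant. An Event Log, which records the reporting source, is completed "When an event is reported from a) resident interview b) staff interview c) interviewer observation, or d) BRDS". No analysis in the plan uses these sources to estimate by arm how much R-REM occurred.

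**The concern.** Aim 2 covers both reporting and recognition. A report count answers the reporting question directly. It answers the recognition question only if occurrence is the same in both arms, and the programme gives reasons to expect that it may not be.

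If staff notice a larger share of fewer events, the count may barely move, and a programme that worked on both fronts would look like a failure of recognition. If the count rises, the plan attributes the rise to awareness and has no stated check on occurrence. At stake is the interpretation of a stated process hypothesis, not the primary result.

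**Working it through.** **1. Stated figures.** The plan gives no effect size, detection rate or sample size for Hypothesis 2, so there is no figure for it to reproduce. The only sample-size figures are for falls, and two of their inputs are borrowed below, so I checked them first. Inputs from Sample size: p0 = 0.33, p1 = 0.2075, two follow-up waves (n = 2), variance inflation 2.5, reliability 0.95, power 80%. Alpha is 0.05, two-sided under Statistical methods. With P = (0.33 + 0.2075)/2 = 0.26875, Q = 1 − P and ρ = 0.5, the Diggle formula gives

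m* = (1.96 × √(2PQ) + 0.842 × √(p0q0 + p1q1))² × 1.5 / (2 × 0.1225²) = 153.3

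and m = 153.3 × 2.5/0.95 = 403.4 (stated 404). The other three results are 430.3 (Diggle, ρ = 0.6; stated 431), and 398.0 and 424.5 (GEE; stated 399 and 425). The falls figures reproduce.

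**2. The identity.** Let detection mean the share of events that staff notice and report. Then

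reported ratio = occurrence ratio × detection ratio.

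One observed number cannot determine two unknowns. Reports are unchanged whenever detection ratio = 1/(occurrence ratio).

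**3. Illustrative values (all assumed).**

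| Occurrence ratio | Detection ratio | Reported ratio |
|---|---|---|
| 0.667 | 1.5 (e.g. 40% to 60%) | 1.00 |
| 0.5 | 2.0 | 1.00 |
| 0.6 | 1.25 | 0.75 |
| 0.9 | 1.75 | 1.57 (1.575) |
| 1.0 | 1.5 | 1.50 |
| 1.5 | 1.0 | 1.50 |

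The last two rows give the same reported ratio for opposite reasons.

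**4. A benchmark from the plan.** The posited falls ratio is 20.75/33 = 0.629. If R-REM occurrence fell by the same ratio (an assumption), reports would rise only if detection rose more than 1/0.629 = 1.59-fold. At 1.5-fold the reported ratio is 0.629 × 1.5 = 0.94.

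**5. Chance of a significant rise.** This is a per-resident proxy (any report, yes or no), not the plan's exact test. Effective n per arm is 525/2.5 = 210, borrowing the falls variance inflation. The base report rate is assumed to be 9.5%, the 30-day verbal aggression figure in the Background. The chance is

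Φ[(pb − pa − 1.96 × √(2P(1−P)/n)) / √(pa(1−pa)/n + pb(1−pb)/n)], with P the mean of pa and pb.

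- Detection ×2, occurrence unchanged: 9.5% against 19.0%, chance about 80%.
- Detection ×2, occurrence ×0.629: 9.5% against 11.95%, about 12.5% (8% to 24% for base rates of 5% to 20%).
- Detection ×2, occurrence ×0.5: 9.5% in both arms, 2.5%.
- Detection ×1.5 alone, or occurrence ×1.5 alone: 9.5% against 14.25%, about 32% in either case.

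**The case against.** Much of the case for the plan stands.

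- **Report volume is a legitimate outcome.** A reader might infer that Aim 2 cannot answer its own question. That goes too far: the counts do measure reporting. The Module 3 test under Aim 1, scored against gold-standard ratings, bears on recognition skill without depending on how much R-REM occurs.
- **The predicted direction has a basis.** The Background reports that the earlier nursing-home evaluation found more recognition and reporting together with fewer falls, accidents and injuries. No hypothesis here says that R-REM itself will fall; that is inferred from the training content and the behavior hypothesis. So the documents do not support a claim that reports will be null, or that the direction is least secure at 12 months.
- **Exact cancellation is a special case.** With detection ratios of 1.25 to 1.75 and occurrence ratios of 0.6 to 0.9, about 75% of that range, weighted evenly, still gives a reported ratio above 1.
- **Sources are not pooled in the Hypothesis 2 test.** A reader might infer pooling from "The data used for evaluation of the primary distal outcome and for R-REM reports include (a) self-report among those residents who are capable". That sentence belongs to the Aim 3 paragraph of Outcomes. The Aim 2 paragraph names only BRDS counts and staff reports.
- **A real rise in mistreatment passing as success** is arithmetically possible, but the documents give no mechanism by which training would cause it. It would need chance imbalance between randomised arms. Six facilities per arm make that possible, and baseline staff reports give some check.
- **R-REM change is not wholly unobserved.** The behavior outcome is a partial proxy.

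None of this supplies an occurrence estimate by arm or a rule for reading a null or a rise as a recognition result. That part of the concern remains.

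**Conclusion.** The concern holds for the recognition inference only. Hypothesis 2 credits a change in reports to awareness, and its tests cannot distinguish a change in detection from a change in occurrence. A null does not show absent recognition, and a rise does not by itself show improved recognition.

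The size cannot be stated. How often the two effects would cancel is unknown, because the documents give neither ratio, and the figures above rest on assumed ratios, an assumed base rate and a variance inflation set for falls. The identity itself needs none of them. Aim 2 is a process aim, and the falls analysis does not change. The plan should be amended because following it as written can mislabel a result, and the data for a better reading are already to be collected.

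**What to change.** 1. **Prespecify an occurrence analysis by arm** at 6 and 12 months, adjusted for baseline and clustering, from sources that do not depend on staff: interviewer observation in all observed residents, and the two-week R-REM-R items in residents able to self-report. State which observation items or Event Log entries count as R-REM. This assumes that observations are made at every wave, as the three-wave design implies.
2. **Limit the Hypothesis 2 conclusion** from BRDS and staff counts to reporting. Draw a recognition conclusion only by reading those counts with the occurrence estimate and its confidence interval, and with the Module 3 gold-standard test. A non-significant occurrence difference must not be taken as evidence of no difference.
3. **Present staff/non-staff agreement by resident as descriptive only.** Its denominator is residents with R-REM after randomisation, which the intervention may change. The instruments also differ: the R-REM-R asks about events aimed at the respondent, and the staff version about events that involve the resident in any role.

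The cost is plan wording, programming and linkage of existing files, with no new data collection. The limits should be stated with the results. Observations are brief, and the R-REM-R misses residents who cannot respond. Interviewers may learn the assignment from staff, as the blinding section concedes. The occurrence estimate will be imprecise.
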